7.2 Assumption checks of secondary outcomes

The following procedures will be done on the final multiple variable logistic regression model:

- Checking influential observations
- Checking multi-collinearity of explanatory variables
- Checking model specifications and perform any necessary interactions
- Testing for overall model goodness of fit

7.3 Adverse Events

Any incidents or accidents which are related to the conduct of this trial including the delivery of the trial intervention, or which affect trial staff while at work will be recorded and copies of the report sent to all three members of the Management Team and the Chair of the Trial Steering Committee. The Chair of the Steering Committee, in consultation with the Management Team, will decide whether any further investigation or action is necessary. There is no external body looking at adverse events.

8 REFERENCES

9 APPENDICES

9.1 Appendix A: SOP for Randomization Meeting

Objectives

- Ensure that all attendants understand the project and the next steps
- To randomly select 4 out of 8 clinics to receive the Nkateko Intervention
- To ensure that the clinic staff and the wider Agincourt population are confident that this process is truly random and is not influenced by any members of the Nkateko team
- To have a written and photographic record of the procedure for use in future papers, talks, etc

Invitees

- 1 member from each of the 8 clinic committees
- Facility manager from each clinic
- Both primary health care supervisors
- Members of the Agincourt Community Advisory Group Non-communicable disease task team
- 1 representative from each village

Prepare beforehand:

- Eight pieces of paper (suggest A5 size) each with the name of one clinic in large letters
- Eight opaque envelopes made from reasonable quality paper (so they will withstand shuffling many times) (
- Flip-chart with eight spaces for writing names, labelled sequentially as 'Clinic 1 Intervention', 'Clinic 2 Comparison', Clinic 3 Intervention', Clinic 4 Comparison' and so on.

Procedure

- Explain Nkateko
- Explain how we will randomise
- Randomisation procedure
 - Make sure everyone can see the eight clinic names and then put each one into an envelope and seal it.
 - Ask at least three (preferably more) different people in the audience to shuffle the envelopes
 - Ask seven people in turn to select an envelope and open it. Each time, as the envelope is opened, fill in the next space on the flip chart. The last space is filled by the remaining clinic
 - o Make a record of the result and take a photo of the completed flip chart.
- Explain next steps

Notes from Nkateko randomisation meeting

DATE: 22 January 2014 VENUE: MRC/Wits Agincourt Offices, Agincourt village PURPOSE: Randomisation of clinics for Nkateko study

Translator – [name] 38 people attended

> Opening prayer and welcome – [name] The Nkateko Project

Overview – [name]

[name] gave a background to the study – using a PowerPoint presentation (available from [name] for reference. He mentioned reasons for the study and that the intervention fits into the new ICDM model. We will need to work with the clinics to make sure that the lay health workers work improves chronic care in the clinics. Our meeting today is to decide which 4 clinics will have lay health workers and which 4 will not.

Evaluation - [name]

Last year we went to find out what is happening in the clinics and we did a population based survey of blood pressure. When the LHWs are in the clinic we will evaluate their work, and then after two years we will go back to the community and do another population based survey to see if their blood pressures have changed. [name] and his team's role is to evaluate the project while [name] will work to develop the LHW intervention

Lay health worker programme – [name]

[name] described what the lay health worker will do in the clinic. Duties might differ between clinics as clinics are different (size, number of staff, business etc). Will workshop with clinic staff to decide how the lay health workers should be working with the clinic staff. [name]'s role in the programme is to develop the work of the LHW in the clinic.

The randomisation process – [name]

[name] explained how we are going to randomise the clinics.

- 1. Reminder that this is research
- 2. We will look at each clinic separately so that we can tell why the programme worked well in one clinic but not in the other if this is the case. This is especially true for this project as the LHW programmes will be different in each clinic.
- 3. We did not want to just decide in the office which clinic to chose, so we are doing it randomly and publicly. Every clinic should have an equal chance to be selected as an intervention clinic.
- 4. Described difference between control and intervention clinics.
- 5. Showed the eight pieces of paper with the clinic names on them
- 6. Showed the 8 unmarked envelopes
- 7. Put one clinic name into its own envelope
- 8. Put all the envelopes into the box
- 9. Two or three people will come and shake the box
- 10. Then we will get 7 people to come up and each chose an envelope.
- 11. First, third, fifth and seventh clinics taken out will be intervention
- 12. Second, fourth, sixth and eight clinics taken out will be control

Everyone agreed that it is a fair process before we started.

- 1. [name] put all the names into envelopes in front of everyone
- 2. All envelopes were put in a box
- 3. A volunteer came up to shake the box
- 4. Audience suggested we fold the envelopes so that they moved more easily in the box
- 5. We opened the box and folded the envelopes smaller
- 6. Second person came and shook the box
- 7. First person chose -
- 8. Another person shook the box

- 9. Second person chose -
- 10. Another person shook
- 11. Third person chose -
- 12. Someone always came up to shake in between another person coming to chose and the results are

Next steps – [name] and [name]

- 1. Advertise for LHWs at clinics and surrounding villages
- 2. Interviews of applicant by Nkateko team and clinic staff and clinic committee
- 3. Appointment
- 4. Workshops with clinics to design the programme
- 5. Training

Closing prayer and refreshments – [name]

9.2 Appendix B: Analysis dummy tables

Variable		Control baseline	Control endpoint	Interventi on baseline	Intervention endpoint	Neither intervention or control Baseline	Neither intervention or control Endpoint
Sex	Male						
	Female						
Age (yrs) me	an (std)						
Marital	In a union						
status	Not in a union						
Highest	No schooling						
Education Attained	Primary						
	Secondary						
	Tertiary						
Household	Most poor						
asset score	Poor						
	Least poor						
Smoking at least every day	Never						
	Previous						
	Less than one a day						
	One or more a day						

Table 1: Comparing	socio-demographi	c variables at baseline	for controls and	intervention clinics
	j socio-ucinographi	c valiables at paseline		

Risk factors		Control baseline Prop (n)	Control endpoint Prop (n)	Intervention baseline Prop (n)		Intervention endpoint Prop (n)
Family history of CVD*	Yes					
(M<55yrs, W<65yrs)	No					
Men's waist circumference M>94cms,	Yes					
	No					
Women's waist	Yes					
circumference W>80cms	No					
Glucose	Below 11 and not fasting					
	Between 6-11 and fasting					
	Above 11					
Self-reported diabetes	Yes and on treatment					
	Yes but not on treatment					
	No					
Total cholesterol	Above 5.1					
	Below or equal to 5.1					
Self-reported corona	ry heart disease					
Self-reported heart failure						
Self-reported Stroke or TIA						
Blood pressure	SDP below 140 and DBP below 90					
	SBP 140 -159 or DBP 90-99					

Table 2: Descriptive clinical data comparing control, intervention, baseline and end of intervention

Risk factors		Control baseline Prop (n)	•	Intervention baseline Prop (n)		Intervention endpoint Prop (n)
	SBP 160 -179 or DBP 100-109					
	SBP 180 + or DBP 110+					

		Control		Intervention		Clinics outside area	
		Usual and last clinic are both control	Usual clinic is control, but last clinic is intervention	Usual and last clinic are both intervention	Usual clinic is intervention but last clinic is control	Usual and last clinic are both outside area, or last clinic is control	Usual clinic is outside area, but last clinic is intervention
Total							
Gender	Female						
	Male						
Age	Under 35						
	35-less 55						
	55 and over						

Table 3: Proportion of individuals for whom the 'usual' clinic was the same as the 'last visited' clinic.

Table 4: Modified South African Guideline: Stratification of cardiovascular risk in patients with hypertension (defined as SBP>139 or DBP>89)

Blood pressure (mmHg)	Presence of risk factors or other conditions							
No risk of hypertension	No risk factors	One or two risk factors	Three or more risk factors or diabetes	Associated clinical conditions				
SBP 140 -159 or DBP 90-99	Low Added Risk	Moderate Added Risk	High Added Risk	Very High Added Risk				
SBP 160 -179 or DBP 100-109	Moderate Added Risk	Moderate Added Risk	High Added Risk	Very High Added Risk				
SBP 180 + or DBP 110+	High Added Risk	Very High Added Risk	Very High Added Risk	Very High Added Risk				

Use Table 4 to allocate individuals to level of risk, which is then used to complete Table 3

Blood pressure (mmHg)	Presence of risk factors or other conditions							
No risk of hypertension	No risk factors	One or two risk factors	Three or more risk factors or diabetes	Associated clinical conditions				
SBP 140 -159 or DBP 90-99								
SBP 160 -179 or DBP 100-109								
SBP 180 + or DBP 110+								

Table 5: Proportion of people with risk factors in the control clinics at baseline

Nkateko Analysis Plan 6th April 2016 final

Blood pressure (mmHg)	Presence of risk factors or other conditions							
No risk of hypertension	No risk factors	One or two risk factors	Three or more risk factors or diabetes	Associated clinical conditions				
SBP 140 -159 or DBP 90-99								
SBP 160 -179 or DBP 100-109								
SBP 180 + or DBP 110+								

Table 6: Proportion of	people with risk factors	in the control clinics	at end of intervention

Table 7: Proportion of	neonle with ris	k factors in the	intervention	clinics at baseline

Blood pressure (mmHg)	Presence of risk factors or other conditions								
No risk of hypertension	No risk factors	One or two risk factors	Three or more risk factors or diabetes	Associated clinical conditions					
SBP 140 -159 or DBP 90-99									
SBP 160 -179 or DBP 100-109									
SBP 180 + or DBP 110+									

Blood pressure (mmHg)	Presence of risk factors or other conditions									
No risk of hypertension	No risk factors	One or two risk factors	Three or more risk factors or diabetes	Associated clinical conditions						
SBP 140 -159 or DBP 90-99										
SBP 160 -179 or DBP 100-109										
SBP 180 + or DBP 110+										

Table 8: Proportion of people with risk factors in the intervention clinics at end of intervention

Table 9: Change in level of cardiovascular risk of study population (primary and secondary outcomes)

Level of	Control			Interventio	n		Statistical Test
	· ·						
cardiovascul	proportion(n))		proportion	1(11)		statistic assessing
ar risk							difference
	Baseline	End	Within	Baseline	End	Within	between cluster
	Prop (n)	Prop (n)	cluster	Prop (n)	Prop (n)	cluster	change and p-
			change			change	value
			and p-			and p-	Value
			value			value	
No or low							
risk							
No risk							
Low risk							
Moderate or							
higher risk							
Moderate							
risk							
High risk							
Very high							
risk							

Repeat for men and women

	Control proportion((n)		Intervention proportion		Statistical Test statistic assessing	
	Baseline Prop (n)	End Prop (n)	Within cluster change and p- value	Baseline Prop (n)	End Prop (n)	Within cluster change and p- value	difference between cluster change and p- value
People with moderate or higher risk***							
Undiagnosed hypertension							
Self-reported blood pressure measured							
Self-reported using medication for hypertension							
Self-reported attended a clinic in the last year.							

Table 10: Changes in hypertension risk, blood pressure, medication and attendance within clusters

Variable		Cont	rol clinic	S		Interv	Intervention clinics		
		1	2	3	4	1	2	3	4
Total number of	of visits								
Number of pat	ients								
Sex	Male								
	Female								
Age	Mean age								
Patient	Visit with 3								
attendance	days of								
(Proportion	appointment								
of visits	Visit NOT								
attended	within 3 days								
within 3 or	of								
less days of	appointment								
appointment	No								
date)	appointment								
Given full set	Yes								
of medication	No								

Table 11: Clinic link record of number of visits by sex, age, patient attendance and availability of medication over 4 time periods (each 5 months long)

9.3 Appendix C: STATA code for computing the primary outcome

* PRIMARY OUTCOME CREATION AND RELATED VARIABLES _____

*Age and sex: men aged over 55 and women aged over 65 have a risk factor for age

gen age= (Vi si tDate - DoB)/365.25 recode age (18/29.999=1 "18-29") (30/39.999=2 "30-39") (40/49.999=3 "40-49") (50/59.999=4 "50-59") (60/69.999=5 "60-69") (70/79.999=6 "70-79") (80/max=7 "80+"), gen(age_grp) | abel (agegrp)

gen AgeRiskGroup=(age>55 & Gender=="M" & age!=. |age>65 & Gender=="F" & age[=.)

tab AgeRiskGroup age_grp

/*Smoking: A smoker will have one risk factor for smoking if he/she
 answers 'yes' to Q20
 answers 'yes' to Q21
 answers 'daily' to question 22

*/

gen smoking=(Q20_EverSmokedCigarettes==1 & Q21_CurrentlySmoking==1 & Q22_SmokingFreqLast30Days<=2 & Q20_EverSmokedCigarettes!=. | Q22_SmokingFreqLast30Days<=2 & Q20_EverSmokedCigarettes!=.)

*Dyslipidemia If cholesterol level in Q35 is > than 5.1mmol/L the person has risk factor for dyslipidemia

gen dysl i pedemi a=(Q34_Total Chol esterol >5.1 & Q34_Total Chol esterol !=.)

/*Family history of CVD. A participant has a risk factor for family history if who

answers 'yes' to Q19 and
either answers 'yes' to Q19b or 'yes' toQ19c

(only one risk factor regardless of how many relatives)

gen family_risk=(Q19_StrokeHeartFMember==1 & Q19_StrokeHeartFMember!=. | Q19_StrokeHeartFather==1 & Q19_StrokeHeartFMember!=. |Q19_StrokeHeartMother==1 & Q19_StrokeHeartFMember!=.)

label var family_risk "Fámily history of CVD"

/*Waist circumference

A man has a risk factor for waist circumference if it is >94cms in Q36
A woman has a risk factor for waist circumference if it is >80cms in

Q36 */ gen waist=(036_WaistCircumference>94 & Gender=="M"|036_WaistCircumference>80 & Gender=="F") gen waist01=. replace waist01=1 if Q36_WaistCircumference<94 & Gender=="M" |Q36_Wai stCi rcumference<80 & Gender=="F" replace wai st01=2 if Q36_Wai stCi rcumference>=94 & Q36_Wai stCi rcumference<102 & Gender=="M" | Q36_Wai stCi rcumference>=80 & Q36_Wai stCi rcumference<88 & Gender=="F" repl ace wai st01=3 if Q36_Wai stCi rcumference>=102 & Q36_Wai stCi rcum Q36_WaistCircumference<112 & Gender=="M"|Q36_WaistCircumference>=88 & Q36_WaistCircumference<98 & Gender=="F" replace waistO1=4 if Q36_WaistCircumference>=112 & Q36_WaistCircumference!=. & Gender=="M" |Q36_WaistCircumference>=98 & Q36_WaistCircumference!=. & Gender=="F"

/*Definition of diabetes (for the purpose of this study)

The definition of diabetes can come either from a recorded high blood sugar or a record of being on treatment for diabetes. So someone has diabetes i f their blood sugar in Q34(?) > 11.1 mmol/L OR • if they have answered 'yes' to Q 4,5 and 6 • and are using one of the drugs listed in questions 6a, b, or c. The person needs to have been told they have diabetes, AND have taken medicine for it in the last two weeks AND the medicine should be one of those listed in Q6a (if it is an 'other drug' then [name] and I will need to make a decision about it). */ gen Q6a_GI i bencl ami de_bi n=(Q6a_GI i bencl ami de<=2) gen Q6a_Gl i cl azi de_bi n=(Q6a_Gl i cl azi de<=2) gen Q6a_Metformi n_bi n=(Q6a_Metformi n<=2) gen Q6_drugs_taken= Q6a_GI i bencl ami de_bi n+Q6a_GI i cl azi de_bi n+Q6a_Metformi n_bi n gen di abetes=(Q35_Gl ucosel nBl ood>11.1 & Q35_Gl ucosel nBl ood! =.) | (Q5_Rai sedBl oodSugar==1 & Q6_drugs_taken>=1) *To calculate mean systolic blood pressure, the first systolic reading will be discarded and then the mean systolic pressure will be calculated as the mean of the second and third readings. The mean diastolic blood pressure and pulse will be similarly calculated. Participants will be grouped according to blood pressure level: 4:Stage two plus hypertension: systolic >180 and/or diastolic >110 3: Stage two hypertension: systolic > 160 and <180 and/or diastolic >100 and <110 2: Stage one hypertension: systolic > 140 and <160 and/or diastolic >90 and <99 1: Normal blood pressure systolic < 140 and diastolic < 90 */ , gen systolic_bp_mean= 0.5*(028a_Systolic2+029a_Systolic3) gen diastolic_bp_mean= 0.5*(028b_Diastolic2+ 029b_Diastolic3) gen heart_rate_mean= 0.5*(028c_HeartRate2+ 029c_HeartRate3) gen bplevel =. replace bplevel=1 if systolic_bp_mean<140 & diastolic_bp_mean<90 replace bplevel=2 if (systolic_bp_mean>=140 & systolic_bp_mean< systolic_bp_mean<160) | (diastolic_bp_mean>=90 & diastolic_bp_mean<100) (diastoirc_pp_mean>=90 & diastoirc_pp_mean<100)
 replace bplevel=3 if (systolic_bp_mean>=160 & systolic_bp_mean<180) |
 (diastolic_bp_mean>=100 & diastolic_bp_mean<110)
 replace bplevel=4 if (systolic_bp_mean>=180 & systolic_bp_mean!=.) |
 (diastolic_bp_mean>=110 & diastolic_bp_mean!=.)
 label define bplabel 1 "Normal blood pressure" 2 "Stage One hypertension"
 3 "Stage Two hypertension" 4 "Stage Two Plus hypertension" label values bplevel bplabel Creation of the minor cvd risk factors variable gen minor_cvd_riskfactors=waist+family_risk+dyslipedemia+smoking+AgeRiskGroup replace minor=. if QOa_InterviewOutcome>2 * Creation of Stroke, Heart Failure and Heart Attack variables gen_stroke_ever=(Q7_EverHadStroke==1 & Q7_EverHadStroke!=. | Q8_EverRecei veStrokeRx==1 & Q8_EverRecei veStrokeRx!=.) gen heart_failure=(Q10_HeartFailure==1 & Q10_HeartFailure!=. | Q11_Recei vedHeartFai I ureRx==1 & Q11_Recei vedHeartFai I ureRx!=.) gen attack_heart=(Q16_HeartAttack==1 & Q16_HeartAttack~=.| Q17_Recei vedHeartAttackRx==1 & Q17_Recei vedHeartAttackRx~=.) * Creation of the associated clinical factors variable gen associated_clinical_factors= stroke_ever+heart_failure+attack_heart

Page 31 of 32

replace associated=. if QOa_InterviewOutcome>2 *Table Two Analysis plan codes gen riskfactors_category=. replace riskfactors=1 if minor_cvd_riskfactors==0 replace riskfactors=2 if minor_cvd_riskfactors>=1 & mi nor_cvd_ri skfactors<=2</pre> replace riskfactors=3 if minor_cvd_riskfactors>=3 & minor_cvd_riskfactors!=. | diabetes==1
replace riskfactors=4 if associated_clinical_factors>=1 & associated_clinical_factors!=. label define risk 1 "No risk factors" 2 "One or two risk factors" 3 "Three or more risk factors or diabetes" 4 "Associated clinical conditions" label values risk risk tab bplevel risk, set type double gen cvdnkateko=. replace cvdnkateko=0 if bplevel==1 | minor_cvd_riskfactors==0 & bplevel!=. replace cvdnkateko=1 if bplevel ==1 & minor_cvd_riskfactors==0 & associ ated_cl i ni cal _factors==0
 repl ace cvdnkateko=2 if (bpl evel ==2 & mi nor_cvd_ri skfactors>=1) & (bpl evel == 2 & mi nor_cvd_ri skfactors<= 2) /// |(bpl evel ==3 & mi nor_cvd_ri skfactors==0)| (bpl evel ==3 & mi nor_cvd_ri skfactors>=1) & (bpl evel ==3 & mi nor_cvd_ri skfactors<=2) repl ace_cvdnkateko=3 if (bpl evel ==2 & mi nor_cvd_ri skfactors>=3 & minor_cvd_riskfactors!=.) /// associated_clinical_factors>=1 & associated_clinical_factors!=.) /// |(bpl evel ==4 & minor_cvd_riskfactors>=1 & minor_cvd_riskfactors<=2)| (bpl evel ==4 & minor_cvd_riskfactors>=3 & minor_cvd_riskfactors!=.) label var cvdnkateko "Levels of CVD Risk Modified SA2015 Nkateko" label define cvdnkateko 0 "No risk" 1 "Low risk" 2 "Moderate risk" 3 "High risk" 4 "Very high risk"

label values cvdnkateko cvdnkateko

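### The Appendix C smoking code never applies two of the three conditions in its own comment, so a component of the primary outcome is defined in two different ways

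*SAP*

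**What the plan says.** Section 5.7 of the SAP points to Appendix C for the Stata commands that create the primary outcome, so the code there is the working definition.

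For smoking, the comment in Appendix C opens "A smoker will have one risk factor for smoking if he/she" and lists three answers: "answers 'yes' to Q20", "answers 'yes' to Q21" and "answers 'daily' to question 22".

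The command beneath it has two branches joined by OR. The first is "gen smoking=(Q20_EverSmokedCigarettes==1 & Q21_CurrentlySmoking==1 & Q22_SmokingFreqLast30Days<=2 & Q20_EverSmokedCigarettes" (not missing). The second is only "Q22_SmokingFreqLast30Days<=2 & Q20_EverSmokedCigarettes" (not missing). Where the two meet, the line reads "Q22_SmokingFreqLast30Days<=2 & Q20_EverSmokedCigarettes!=. | Q22_SmokingFreqLast30Days<=2 & Q20_EverSmokedCigarettes" (not missing).

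The result feeds the risk-factor count: "gen minor_cvd_riskfactors=waist+family_risk+dyslipedemia+smoking+AgeRiskGroup". In Table 2 of section 6.1, the number of risk factors and the blood pressure band together set the level of added risk. Moderate or higher counts as the primary outcome.

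**The concern.** The comment and the command should classify every participant alike, and they do not. The comment asks for someone who has ever smoked, smokes now and smokes daily. As written, the command asks only for a low Q22 code and any recorded answer to Q20. An analyst working from the comment and one running the code could put the same person in different categories.

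This matters most at one boundary. In Table 2, a person with SBP 140-159 or DBP 90-99 and no risk factor is at low added risk; with one risk factor the same person is at moderate added risk. For someone with no other minor factor, no diabetes and no associated clinical condition, the smoking variable alone then decides whether the primary outcome is 0 or 1. Elsewhere in Table 2 an extra factor can change the level without changing the binary outcome. Examples are two to three factors at SBP 140-179 or DBP 90-109, and none to one at SBP 180 or above or DBP 110 or above. Those shifts touch secondary outcome d in section 2.2.2.

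**Working it through.** The SAP states no figure here, so the check is of logic.

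**Inputs, all from Appendix C.** Write
- A: Q20 = 1 (ever smoked)
- B: Q21 = 1 (currently smoking)
- C: Q22 <= 2 (frequency in the last 30 days)
- D: Q20 is not missing

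**Step 1, reduction.** In Stata, AND binds before OR, so the command reads (A and B and C and D) or (C and D). Whenever the first branch is true, the second is true as well. The expression is therefore C and D, and A and B never alter the result.

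**Step 2, enumeration.** Assumed coding: Q20 and Q21 take 1 (yes), 2 (no) or missing; Q22 takes 1, 2, 3 or missing. Stata treats missing as larger than any number, so a missing Q22 fails the test. That gives 3 × 3 × 4 = 36 combinations. The command agrees with C and D in all 36. It returns smoker in 2 (Q20 values) × 3 (Q21 values) × 2 (Q22 values) = 12. The written definition returns smoker in 1 combination if only code 1 means daily, and in 2 if codes 1 and 2 both do. The disagreements number 12 − 1 = 11 or 12 − 2 = 10, and in each the code says smoker where the comment does not. Without the second branch the command returns smoker in 2.

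**Step 3, dependence on the questionnaire.** The SAP gives neither the Q22 code list nor the skip pattern, so each case is shown.

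| Who was asked Q22 (assumed) | Possible combinations | Disagreements if daily = code 1 | Disagreements if daily = codes 1 and 2 |
|---|---|---|---|
| Everyone | 36 | 11 | 10 |
| Only those with yes to Q20 | 18 | 5 | 4 |
| Only those with yes to Q20 and Q21 | 12 | 1 | 0 |

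In the second row the command returns smoker in 1 × 3 × 2 = 6 combinations, so the differences are 6 − 1 = 5 and 6 − 2 = 4. The four that remain are ever-smokers whose Q21 is no or missing and whose Q22 code is 1 or 2. In the third row the OR branch changes nobody, and the one possible disagreement is Q22 = 2 when only code 1 means daily.

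These counts are answer patterns, not people. They show where comment and code can differ, not how often.

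**The case against.** The strongest reply is that a redundant test is not a wrong classification. If the questionnaire sent only current smokers to Q22, everyone else has it missing, fails the test and is correctly coded 0. A person who denies smoking now yet reports frequent smoking in the last 30 days has probably answered inconsistently, and section 5.3.1 describes consistency checks in the field and at data entry. It does not say whether they cover the smoking items. This reply stands as a limit on the consequence. It does not remove the contradiction between comment and command.

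The second reply concerns the threshold. Codes 1 and 2 may both be daily categories. Dummy Table 1 in Appendix B separates less than one a day from one or more a day, but it does not give the Q22 codes. This also stands: the threshold is an unresolved mismatch, not a proven error.

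Two stronger readings are tempting. A reader might infer a measurable overstatement of prevalence. Suppose 20% of the sample is in the lowest hypertensive band, 10% to 30% of those have no other factor, and 5% to 20% of those are misclassified. The product runs from 0.20 × 0.10 × 0.05 = 0.1 percentage points to 0.20 × 0.30 × 0.20 = 1.2 points. None of these rates is in the SAP, and the range leaves out zero, which is a live possibility. A reader might also infer bias in the treatment effect. The primary outcome is a change between two surveys, compared between arms, and the same command is run on all four groups. A shift of similar size in each would largely cancel, and nothing in the SAP points to a difference by arm or survey.

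**Conclusion.** The contradiction is certain from the text: two of the three written smoking conditions have no effect in the command that builds the primary outcome. The wider Q22 threshold is a further mismatch, which only the code list can settle. Anyone with Q22 at 2 or below and Q20 recorded, who did not answer yes to both Q20 and Q21, is counted as having a risk factor. At SBP 140-159 or DBP 90-99 this can move them into the primary outcome.

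The number affected cannot be computed from the SAP. It is zero if Q22 was asked only of people with yes to Q20 and Q21 and codes 1 and 2 both mean daily. Otherwise it depends on how many participants fall into the disagreeing patterns. The error is common to arms and surveys, so the documents support a defect in the definition, not a demonstrated misclassification or a biased contrast. It should be corrected because it sits in the primary outcome and the repair is small.

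**What to change.** 1. Delete the branch after the OR, so that all three conditions apply.
2. Check the Q22 code list, restrict the test to the code or codes that mean daily, and name them in the comment.
3. Code smoking as 0 when Q20 or Q21 is no. Set it to missing only when an answer that should have been given is absent: Q20 itself, Q21 after yes to Q20, or Q22 after yes to both.

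The third step needs care. The risk-factor count is a plain sum, so one missing term makes the whole count missing. If smoking became missing whenever Q21 or Q22 is blank, never-smokers who properly skipped them would lose their count and drop out of the complete-case analysis that section 5.5 makes the main one.

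The cost is a few lines of Stata and a look at the questionnaire, with no new data. Section 5.3.2 still gives the database freeze date as to be confirmed. A cross-tabulation of the old and new smoking variables, pooled over clinics to keep the blinding, would show how many people change.

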5.5 Methods for withdrawals, loss to follow-up and Missing Data

We will not have withdrawals nor loss to follow-up since this is a survey cross-sectional design. However, participants selected for the sample may not be present when we visit the household the first time, in which case we will carry out up to two more call backs. In the case where field call backs and tracing have not been successful to ensure all key data have been collected, multiple imputation methods will be used to generate outcomes. For example, blood pressure level might be missing for some cases. We will conduct a complete case analysis and also an analysis where missing blood pressure levels are imputed (imputed analysis) and compare whether there are apparent variations in the results obtained. The same applies for other key variables like self-reported hypertension.

Multiple imputation methods for cluster randomised trials with few clusters are not well developed, although this is a growing research field. A systematic review done recently showed none of the studies reviewed had a multiple imputation procedure that handled clustering and very few techniques also used these in regression models that truly adjusted for the clustering effect⁷. We intend to implement some of these procedures in our analysis as part of sensitivity analysis, but the main analysis will be based on the complete cases.

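### The primary-outcome code in Appendix C counts a missing waist as a risk factor and joins family history by OR where its own definition requires AND, so people near the outcome boundary can be misclassified

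*SAP*

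**What the plan says.** SAP 5.7 points to Appendix C for the commands that generate the primary outcome, so that code is the working definition of the endpoint.

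- **Waist.** The indicator is "gen waist=(036_WaistCircumference>94 & Gender=='M'|036_WaistCircumference>80 & Gender=='F". (036 for Q36 is taken as a text-reading artefact.) A second, graded waist variable in the same block does exclude missing values at its top level: "Q36_WaistCircumference>=112 & Q36_WaistCircumference!=. & Gender=='M". The graded variable does not enter the count.
- **Family history.** The comment requires a yes to Q19 and, in addition, that the person "either answers 'yes' to Q19b or 'yes' toQ19c". The code begins "gen family_risk=(Q19_StrokeHeartFMember==1 & Q19_StrokeHeartFMember!=. | Q19_StrokeHeartFather==1" and adds the mother item with a further OR.
- **Count.** The five indicators are added: "gen minor_cvd_riskfactors=waist+family_risk+dyslipedemia+smoking+AgeRiskGroup". The only rule that sets this sum to missing depends on the interview outcome code, not on whether single items are missing.
- **Missing data.** SAP 5.5 plans imputation as a sensitivity analysis, "but the main analysis will be based on the complete cases". SAP 5.6 has implausible values entered as missing.
- **Boundary.** Under SAP 6.1, SBP 140-159 or DBP 90-99 is an event only with at least one risk factor. From 160 or 100 upward it is always an event.

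**The concern.** In the lowest hypertensive stage, one risk factor separates low from moderate added risk, and that is the boundary of the primary outcome. A waist that was never measured, or was set to missing as implausible under 5.6, can supply that factor. So can a yes to Q19 with neither parent affected. Both errors turn a non-event into an event. A missing cholesterol value acts the other way: it is read as normal, and a true event may be lost.

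For risk-factor items the code therefore fills in one fixed value, 1 for waist and 0 for the others, where 5.5 announces complete cases. The family-history error needs no missing data at all. The outcome is a change between two surveys, so any difference between surveys or arms in these patterns would enter the effect estimate.

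**Working it through.** The SAP states no figure on this point to reproduce. The check evaluates the printed expressions, with numeric missing larger than any number and AND evaluated before OR.

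**1. Each indicator when its item is missing**

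| Item missing | Code returns |
|---|---|
| Waist, man or woman | 1 |
| Cholesterol | 0 |
| Age | 0 |
| Smoking (Q20 or Q22) | 0 |
| Family history (Q19) | 0 |
| Glucose, no treated self-report (diabetes indicator) | 0 |

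**2. Family history: code against written definition.** Q19b and Q19c are taken to be the father and mother items. This is inferred from the variable names.

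| Q19 | Father | Mother | Definition | Code |
|---|---|---|---|---|
| yes | no | no | 0 | 1 |
| no | yes | yes | 0 | 1 |
| no | yes | no | 0 | 1 |
| no | no | yes | 0 | 1 |

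These are the 4 of 8 yes/no patterns that disagree. With missing as a third answer, 9 of 27 disagree, always with code 1 and definition 0. Only the first row needs no inconsistent answers. If a parent yes always comes with a Q19 yes, the code reduces to Q19 alone.

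**3. Effect of one extra risk factor on the binary outcome (rule in 6.1)**

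| Blood pressure | 0 to 1 factor | 1 to 2 factors |
|---|---|---|
| Normal | 0 to 0 | 0 to 0 |
| 140-159 or 90-99 | 0 to 1 | 1 to 1 |
| 160-179 or 100-109 | 1 to 1 | 1 to 1 |
| 180 or 110 and above | 1 to 1 | 1 to 1 |

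Only the lowest stage with nothing else present can flip. Diabetes or an associated condition already makes such a person an event under Table 2.

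**4. Size, on assumed inputs.** The SAP gives neither the share of people in the lowest stage nor item missingness.

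Shift in prevalence = s × q × m, where s is the share in the lowest stage, q the share of those with no other factor, and m the share of those affected by the error.

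- Waist, s = 10-20%, q = 30%, m = 5-15%: 0.10 × 0.30 × 0.05 = 0.15 points, up to 0.20 × 0.30 × 0.15 = 0.9 points.
- Family history, same s and q, m = 10-30%: 0.10 × 0.30 × 0.10 = 0.3 points, up to 0.20 × 0.30 × 0.30 = 1.8 points.
- Alternative set for either error, s = 15-25%, q = 10-30%, m = 1-10%: 0.15 × 0.10 × 0.01 = 0.015 points, up to 0.25 × 0.30 × 0.10 = 0.75 points. On the 3905 baseline respondents (5.11) that is about 1 to 29 people.

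**5. From prevalence to effect.** With d the shift in each survey-by-arm cell, the bias in the between-arm difference in change is (d at end − d at baseline, intervention) − (d at end − d at baseline, control). Equal shifts give 0. If m for waist were 15% in one cell and 5% in the other three, with s = 20% and q = 30%, the bias would be 0.20 × 0.30 × (0.15 − 0.05) = 0.6 points. SAP 3.5 plans for an absolute difference of about 11 points.

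**The case against.** The strongest reply is that the practical effect is small and mostly cancels. The same code runs on all four survey-by-arm cells, 5.3.1 describes repeated completeness checks with forms returned to the field, and only a narrow group can flip. This stands as a limit on size. It does not make the two lines right.

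A reader might infer four stronger points that the document does not support:

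- **That imputation has nothing to work on.** Missing blood pressure, the example in 5.5, stays missing in the code. Raw waist, cholesterol and glucose also stay missing and could be imputed before the indicators are derived.
- **That missing glucose turns events into non-events.** The diabetes indicator does become 0, but diabetes is not one of the five summed factors, and the lines that assign the upper risk levels are broken in the text at hand. Its path to the final outcome cannot be traced.
- **That every missing item coded as absent is an error.** Smoking frequency, the parent items and the diabetes drug items may be skipped after a no to the lead question. The questionnaire is not shown. For a legitimate skip, absent is correct.
- **That the treatment effect is biased.** This needs missingness or family history to differ by survey or arm, and nothing in the SAP shows that it does.

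It is also fair to object that setting every component to missing would do harm. The count is a plain sum, so one missing item makes it missing, and the printed moderate-risk lines would then not classify a person at 160-179 or 100-109.

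**Conclusion.** Two lines are wrong as written. The waist indicator codes missing as present, and the family-history code contradicts the definition printed beside it. In addition, missing measured items such as cholesterol are read as absent, which does not match the complete-case rule in 5.5 for risk-factor items. Missing blood pressure is handled consistently with 5.5.

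The binary primary outcome is affected only in the lowest hypertensive stage with no other risk factor, diabetes or associated condition. For other hypertensive people the errors can at most move the risk level, which is secondary outcome (d). The size cannot be computed from the SAP. Under the assumptions above it is probably below about 1 to 2 percentage points of prevalence per error, and less in the between-arm change unless the pattern differs by survey or arm. The case for correcting it is that the primary-endpoint code departs from its own definition and from the stated missing-data rule, and not that a large bias has been shown.

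**What to change.** Before the database freeze, whose date 5.3.2 leaves open:

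1. **Waist.** Add `& Q36_WaistCircumference!=.` to both the male and the female branch, or set waist to missing when Q36 is missing. The guard alone turns missing into absent, so it must go with step 3.
2. **Family history.** Reconcile code and definition. If the comment is what was intended, code Q19==1 & (father==1 | mother==1). If Q19 alone was intended, change the comment. In either case, state how the age limits beside family history in dummy Table 2 (Appendix B) are applied, since neither the comment nor the code contains them.
3. **Binary outcome.** Derive it directly, so that normal blood pressure stays 0 and 160/100 or above stays 1 whether or not the count is missing. In the lowest hypertensive stage, set it to 1 if any risk factor, diabetes or associated condition is observed. Set it to missing if none is observed and a measured item (waist, cholesterol) or a lead question is missing. Otherwise set it to 0.
4. **Skipped questions.** Treat follow-up questions legitimately skipped after a no as no.
5. **Reporting.** Tabulate item missingness by survey and arm, so that any differential pattern is visible.

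The cost is some recoding, including the block that assigns risk levels if components are set to missing, and slightly fewer complete cases.
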